6.4. Secondary Endpoint Analysis

The secondary endpoints will first be summarized by treatment group using mean and standard deviation. We will use similar adjusted regression methods for the secondary endpoints as for the primary endpoints described in Section 6.3.2. Details are described as follows.

- For the percent change (relative to the measure at the end of Phase 2) of the biomarker measured repeatedly (weeks 4, 8, 12), we will use linear mixed effects models (Verbeke and Molenberghs, 2000). Fixed effects in the model will include: treatment group, visit, treatment group by visit interaction, study site, whether the visit time is pre-COVID or not (as a time-dependent covariate), and any baseline characteristics (listed in Section 6.2) which are different at $p<0.20$. A random intercept for each subject will also be included in the model to account for within subject correlation.
- For study cigarette smoked, similar analyses to total cigarettes per day will be performed.
- For the abstinence outcome, we will use logistic regression.

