3.2. Secondary Endpoints

- Biomarker: percent change in biomarker, CEMA at the weeks 4, 8 and 12 visits during Phase 3 as compared to the last visit in Phase 2.
- Study Cigarettes per day (CPD): the mean study cigarettes smoked per day based on 7 days' Daily Interactive Voice Response (IVR)-Revised data before the week 12 visit.
- Seven-day abstinence and CO ≤ 6ppm for all 7 days before the week 12 visit.

3.3. Exploratory Endpoint:

- Non-combusted tobacco/nicotine products use: the number of days using any non-combusted tobacco/nicotine products in Phase 3.
- Characteristics' of products chosen (type, flavor, nicotine strength)
- Biomarkers: percent change in biomarkers (Total Nicotine Equivalents, total NNAL, mercapturic acids other than CEMA) at the weeks 4, 8 and 12 visits during Phase 3 as compared to the last visit in Phase 2.
- Product satisfaction (Product Evaluation Scale if they used the product since the last visit; Cigarette Evaluation Scale if they smoked cigarettes since the last visit)
- Perceived health risk (Phase 1, Phase 2 and end of week 12 of Phase 3: all products for all subjects)
- Measures of discomfort/dysfunction: MNWS-R, QSU, CESD (NNC vs VLNC cigarettes irrespective of use of products)
- Dependence (FTND, WISDM, PATH items; monthly for study cigarettes)

3.4. Safety Endpoints:

- Potential adverse consequences: Change in mental (CES-D) or physical health (heart rate, blood pressure, weight)
- Increased TNE (corrected by creatinine), calculated as change from Phase 1 baseline.
- Adverse events and Serious Adverse events

4. Intervention

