16.6.4. Secondary Endpoint Analysis

The secondary endpoints will first be summarized by treatment group using mean and standard deviation. We will use similar adjusted regression methods for the secondary endpoints as for the primary endpoints described in Secondary Analysis Section. Details are described as follows.

- For the percent change (relative to the measure at the end of Phase 2) of the biomarkers measured repeatedly (weeks 4, 8, 12), we will use linear mixed effects models.⁶¹ Fixed effects in the model will include: treatment group, visit, treatment group by visit interaction, and study site, whether the visit time is pre-COVID or not (as a time-dependent covariate), and any baseline characteristics (listed in Section 16.6.2) which are different at $p>0.20$. A random intercept for each subject will also be included in the model to account for within subject correlation.
- Study cigarettes per day will be similar to the Primary Endpoint analyses for total cigarettes per day.
- For the smoke-free point prevalence outcome, we will use logistic regression.

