5.2. Secondary Endpoints

- Biomarker: percent change in biomarker, CEMA, at the weeks 4, 8 and 12 visits during Phase 3 as compared to the last visit in Phase 2.
- Study cigarettes per day (CPD): the mean of study cigarettes smoked per day based on 7 days' Daily IVR-Revised data before the week 12 visit.
- Seven-day abstinence: if total CPD=0 for all 7 days before the week 12 visit and CO \leq 6ppm at week 12.

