6.2. Describing the Study Population

Descriptive statistics will be performed for data collected at different visits. Daily Interactive Voice Response (IVR) data will be summarized by phase and by visit (according to the actual visit dates or scheduled visit dates if a visit is missed). Baseline data will be compared between the two studied conditions with t test or Wilcoxon rank sum test

for continuous variables and chi-square test or Fisher's exact test for categorical variables, which include sex, age, race, education, menthol status, dependence (FTND), CPD, nicotine metabolite ratio (NMR), and TNE. Baseline CPD and TNE are based on Phase 2.

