6.3.2. Secondary Analysis

For the Week 12 CPD and total number of smoke-free days, we will perform an adjusted analysis, adjusting for baseline value, study site (the randomization stratification factor), whether the Week 12 visit is pre-COVID or not, and any baseline characteristics (listed in Section 6.2) which are different at $p<0.20$, in multivariable regressions to improve efficiency.

For the CPD outcome measured repeatedly, we will use linear mixed effects models (Verbeke and Molenberghs, 2000). Fixed effects in the model will include: treatment group, visit, treatment group by visit interaction, baseline CPD, study site, whether the visit time is pre-COVID or not (as a time-dependent covariate), and any baseline characteristics (listed in Section 6.2) which are different at $p<0.20$. A random intercept for each subject will also be included in the model to account for within subject correlation.

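### The CEMA model leaves out baseline CEMA; the test is valid, but adding this already collected covariate buys a modest gain in precision at almost no cost

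*Combined protocol and SAP*

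**What the plan says.** The endpoint in SAP 5.2 is "percent change in biomarker, CEMA, at the weeks 4, 8 and 12 visits during Phase 3", relative to the last Phase 2 visit; protocol 3.2 and 16.5.2 agree.

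SAP 6.4 opens with a general statement: "We will use similar adjusted regression methods for the secondary endpoints as for the primary endpoints described in Section 6.3.2". It then gives the biomarker model in detail: "Fixed effects in the model will include: treatment group, visit, treatment group by visit interaction, study site", a time-dependent pre-COVID indicator, and characteristics from Section 6.2 that differ between arms at p<0.20, with a random intercept per subject. Protocol 16.6.4 gives the same list, again without baseline CEMA.

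The Section 6.2 list is "sex, age, race, education, menthol status, dependence (FTND), CPD, nicotine metabolite ratio (NMR), and TNE". It holds baseline CPD and TNE but not CEMA.

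For the repeated-CPD model, SAP 6.3.2 lists "treatment group by visit interaction, baseline CPD, study site". The baseline value is also named in both primary analyses (SAP 6.3.1), in the adjusted analyses (6.3.2), and for days of non-combusted product use (6.5).

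The stated summary by arm is: "The secondary endpoints will first be summarized by treatment group using mean and standard deviation". SAP 6.5 passes the biomarker method on to TNE, NNAL and the other mercapturic acids. Which visit contrast is tested is not stated.

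**The concern.** Baseline CEMA enters only as the denominator of percent change. Dividing by baseline does not adjust for it: a participant whose end-of-Phase-2 reading happened to be high will tend to show a fall with no treatment effect, and one with a low reading a rise. That regression to the mean is noise in the outcome, and a baseline term removes part of it.

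At stake is the precision of the highest-ranked endpoint bearing on the hypothesis of less toxicant exposure in protocol 1.1. Reproducibility is a smaller matter. The opening sentence of SAP 6.4 could be read to include a baseline term and the explicit list to exclude it, so two analysts could fit different models.

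There is also a reporting point. For right-skewed data, the arithmetic mean percent change can be positive in an arm whose typical exposure fell, so the mean and SD should not stand alone.

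**Working it through.** **The plan's own figures.** The documents state no power, SD, correlation or effect for CEMA, so there is no CEMA figure to reproduce. The primary-endpoint power does reproduce, which confirms the reading of sample size and attrition. At N=400, n = 0.8 × 400/2 = 160 per arm. For smoke-free days the NNC rate is .0504 and the VLNC rate is .0504 + 11/84 = .1814, so power = Φ(.1310/√(.2318/160) − 2.241) = Φ(1.20) = .885, against the stated .88. At N=450 and 500 the results are .920 and .946, against .92 and .94.

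**Analytic guide.** On the log-change scale with equal SDs and baseline-to-follow-up correlation ρ, the unadjusted change has variance 2σ²(1−ρ) and the baseline-adjusted value σ²(1−ρ²). The ratio is (1+ρ)/2: .75 at ρ=.5 and .85 at ρ=.7. This gives the direction, but the planned scale is percent change, so that was simulated.

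**Simulation.** From the plan: 200 per arm, 20% attrition, visits at weeks 4, 8 and 12, two-sided .05, random-intercept model with visit and treatment by visit. Assumed: log-normal CEMA, exchangeable log-scale correlation, dropout of 6.7%, 13.3% and 20% by the three visits, a 25% fall, nobody stopping smoking, and 4,000 trials per row (Monte Carlo SE at .78 is √(.78×.22/4000) = .007). Site, the pre-COVID term, the p<0.20 covariates and multiple imputation were not modelled.

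| log-SD, ρ | Three-visit average: planned → + log baseline | Week 12: planned → + log baseline | Expected mean % change in an arm with a typical 25% fall |
|---|---|---|---|
| 1.0, .5 | .779 → .875 | .519 → .569 | .75·e^.500 − 1 = +24% |
| 1.0, .7 | .968 → .983 | .820 → .861 | .75·e^.300 − 1 = +1% |
| 0.8, .5 | .958 → .992 | .786 → .858 | .75·e^.320 − 1 = +3% |
| 0.7, .5 | .988 → 1.000 | .902 → .949 | .75·e^.245 − 1 = −4% |
| 0.7, .7 | 1.000 → 1.000 | .992 → .997 | .75·e^.147 − 1 = −13% |

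The last column is ratio × exp(SD²(1−ρ)) − 1.

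- **Variance.** Over 36 settings, the treatment-effect variance without the covariate was 1.13–1.34 times as large (three-visit average) or 1.08–1.20 times (week 12).
- **Larger trial.** At 225 per arm the first row becomes .82 → .91.
- **Larger effects.** For a 40% fall, planned three-visit power is at least .997; the lowest week-12 result is .938 → .961.
- **Raw baseline.** Untransformed baseline gives .807 in the first row, against .875 for log baseline.
- **Type I error.** Three-visit average: .045–.055 as planned, .044–.061 with log baseline.
- **Loss.** Adding log baseline did not lower power in any setting.

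**Independent check.** A simpler simulation (175 evaluable per arm, each participant's three-visit mean, ordinary least squares) gave .78 → .88, .97 → .99, .99 → 1.00 and 1.00 → 1.00 for rows 1, 2, 4 and 5.

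**Subgroups.** SAP 6.6 repeats the analysis at α/2, which is .025 for CEMA. For women (44.7% of 175, about 78 per arm) the same simpler simulation gave .35 → .47, .62 → .71, .72 → .88 and .94 → .98 for the same four rows.

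**The case against.** The strongest points on the other side:

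- **The parallel is loose.** CPD is modelled as an absolute value, so its baseline term is its only link to baseline; CEMA is already relative to baseline, and the omission may be deliberate. This explains the omission, but a denominator does not do the work of a covariate.
- **The general wording may cover it.** SAP 6.3.2 adjusts for baseline and SAP 6.4 promises similar methods. That is possible. If so, the edit only records the intention, because the explicit list says otherwise.
- **Much of the gain comes from the log transform.** This stands. The literal counterpart of the CPD model, raw baseline, lifts the most favourable setting by about 3 points rather than 10. Log baseline is therefore the term to add.
- **The three-visit average is not a stated contrast.** This also stands. At week 12 the gains at a 25% fall are about 0.5 to 7 points.
- **The inputs are assumed, and the effect may be large.** The plan's CPD assumption, 15 to 7, is a 53% fall; at that ratio planned power is at least .998 and the covariate adds nothing of note in the full sample.
- **Missing baselines.** With intention-to-treat analysis and multiple imputation, a participant without baseline CEMA would be imputed rather than dropped. The covariate then comes from the same imputed data sets.

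**Conclusion.** The concern holds. Baseline CEMA is absent from the model in both documents, the p<0.20 rule cannot supply it, and the plan names the baseline value in its primary, repeated-CPD and non-combusted-use models. Validity is not in question: type I error is near .05 with or without the term, and no primary conclusion depends on it.

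The gain is modest. Without log baseline the treatment-effect variance is roughly 10% to 35% larger on the three-visit average and 10% to 20% larger at week 12. It matters for power only if CEMA is variable and the effect moderate, or in the subgroups. These sizes rest on an assumed log-normal distribution, log-SD, correlation and effect, none of which the documents give. The case for the change is that the gain costs almost nothing, rather than that it is large.

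**What to change.** In the biomarker bullet of SAP 6.4 and of protocol 16.6.4, add the log of the end-of-Phase-2 value of the biomarker to the fixed effects, and include it in the imputation model. Keep percent change as the outcome, so that no endpoint definition changes. The method then carries over to TNE, NNAL and the other mercapturic acids. The protocol bullet needs correcting in any case: it selects covariates at p>0.20 where the SAP has p<0.20.

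Useful but optional additions:

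- Name the contrast tested: the average of weeks 4, 8 and 12, or week 12.
- Report the median percent change and quartiles by arm beside the mean and SD.
- Pre-specify a supportive model of log biomarker with log baseline, reported as a ratio of geometric means, with values below the detection limit set to LOD/√2. It should not replace the planned analysis. If 10% in each arm stop smoking and fall to 3% of their usual CEMA, its power for a 25% fall in continuing smokers is .63–.71, against .69–1.00 for the planned model.

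The covariate costs a change of wording in two bullets and one degree of freedom. It needs no new data, since first-void urine is collected at visit 00 (protocol 5.2.4) and mercapturic acids are scheduled there (protocol 27). The sample size does not change. The edit should be made before outcome data are analysed.

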6.5. Exploratory Endpoint Analysis

- For the number of days of non-combusted tobacco/nicotine products use, we will use Poisson or negative binomial regression, adjusting for baseline value, study site, whether the visit is pre-COVID or not, and any baseline characteristics which are different at $p < 0.20$.
- We will descriptively examine the characteristics of the various products that are chosen (type, nicotine strength, flavor).
- For other biomarkers, similar analyses to Secondary Endpoint will be performed.
- Product satisfaction (Product Evaluation Scale, Cigarette Evaluation Scale) at the first time a participant tried a product will be summarized using mean and standard deviation and compared between two treatment arms using linear regression.
- Repeated measures of perceived health risk will be analyzed using the mixed effects model as described in Section 6.3.2.
- Discomfort as assessed by MNWS-R, QSU, CESD will be compared between the VLNC vs. NNC cigarette conditions. The methods for comparing discomfort measures between VLNC and NNC cigarettes will be the same as for those described for the primary endpoints in Section 6.3.
- Repeated measures of dependence of study cigarettes will be analyzed using mixed effects model described in Section 6.3.2.
- We will examine the cross-sectional associations of non-combusted products use with cigarettes smoked and biomarkers at different visits using marginal generalized estimating equations (GEE) model (Diggle et al, 2002, Chapter 12) with the non-combusted product use as the independent variable.
- We will explore baseline predictors of responses. We will use multivariable regressions to determine predictors of product use patterns, e.g., non-combusted product use, combusted product use, and smoke-free days. Predictor variables (depending on the responses measured) will include baseline CPD, total nicotine equivalents, FTND, age, sex, racial ethnic group, SES, perceived risk of products, product expectancy, product utility, social and environmental influences, contemplation ladder, menthol cigarette use, and nicotine metabolite ratio (NMR, reflecting rate of nicotine metabolism). Similar regression models as described in Sections 6.3 and 6.4 will be used.

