content of cigarettes was withheld. These study designs, while able to evaluate the influence of nicotine reduction per se on relevant outcomes, do not adequately simulate a real world marketplace in three major ways. First, with a national nicotine reduction policy, no regular nicotine cigarettes would be available and alternative nicotine-containing products would be widely available. Therefore, the impact of such a policy on the use of other tobacco or nicotine products needs to be considered to fully understand public health effects. Second, providing cigarettes for free is likely to underestimate the degree to which RNC cigarettes might impact smoking behavior. If smokers were required to pay \$6 to \$10 for a pack of cigarettes that they find relatively non-rewarding, they are likely to smoke fewer cigarettes than they would if these products are provided at no cost.¹⁴ The importance of price on consumption is widely known and is the basis of increasing taxes on cigarettes to drive the prevalence of smoking down.¹⁵ Third, with the implementation of a reduced nicotine policy, the FDA would by necessity provide information to consumers on the reduced nicotine content of cigarettes. The knowledge of nicotine content in cigarettes might influence expectancies or beliefs about the cigarettes, which then might affect smoking uptake or behavior. With respect to simulating the consumer, another limitation of prior studies is the recruitment of a relatively narrow selection of smokers in most studies. That is, smokers were recruited only if they were not motivated to quit smoking and used minimal amounts of other tobacco products. In a recent large clinical trial, about 15% were excluded for using other tobacco products (e.g., greater than 9 times per month) and 7% were excluded because they were motivated to quit in the next 30 days, thus omitting almost a quarter of the sample. All these limitations demonstrate the need to conduct a study that includes a more broadly selected sample of smokers and that better approximates the marketplace that is likely to occur if the policy to reduce nicotine in cigarettes is implemented.

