Purchasing power. Each subject will be given a point voucher at each marketplace visit that can be exchanged for products. Points provided at each visit are based on the subject's points per day multiplied by the number of days till their next scheduled visit. Subject's points per day are constant throughout the study and are calculated to allow the subject to cover their baseline cigarettes and other nicotine product use (e.g., vaping device, smokeless tobacco or nicotine replacement therapies) per day plus 1 point per day to allow for experimentation in the marketplace. Participants will receive a coupon that can be applied to discount e-cigarettes and/or medicinal nicotine products in the marketplace. This will allow for experimentation with the more expensive e-cigarette devices or a large box of medicinal nicotine. This coupon cannot be used on cigarettes or smokeless tobacco/snus/nicotine pouches. This coupon can only be used one time per participant. The participant cannot exchange the coupon for cash at the end of the study. Although the need for higher voucher point amounts to take into account the possibility of compensatory smoking may be a concern, to date, the majority of people do not increase in smoking resulting from availability of VLNC cigarettes. In order to discourage needless exchange of vouchers for products, any portion of the voucher not used at each visit can be banked and used at later visits or converted to cash (up to \$200) at the end of the study. Unopened products will be reimbursed for the amount of points exchanged for the product.

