- 14) Cigarette (Usual Brand)/Product Purchase Task (Week 92 only).

B.2. Administered as an interview by the Research Assistant (entered into REDCap):

- 1) Health Changes Questionnaire.
- 2) Adverse Events.
- 3) Concomitant Medications.
- 4) IVR Review of Daily Call and follow-up on missing and unusual reports.
- 5) Timeline Followback Questionnaire (14 days for Visit 93 or since last visit for Visit 92).
- 6) Recreational Drug Use Questionnaire (1 month version at Visit 93).
- 7) Study Product (see C.1-3: Visit 92 only) and Procedure Compliance Review.
- 8) End of Visit Evaluation.

C. Introduction to Experimental Marketplace with Usual Brand Cigarettes:

Upon completion of V92 (end of Baseline), subjects will have access to the web-based experimental marketplace that includes their usual brand cigarettes and non-combusted tobacco and nicotine products. This phase is instituted to allow the participant to adjust to the experimental marketplace while smoking usual brand cigarettes prior to randomization

to study cigarettes. In addition, exploratory comparisons will be made between Phases 1 and 2 to assess purchasing and product use patterns when participants are purchasing their own cigarettes in the natural environment versus when purchasing products in the experimental market.

C.1 Present marketplace web page

Subjects will be presented with the Marketplace web page containing their usual brand cigarettes and the other study tobacco and nicotine products (no study cigarettes). These products include: smokeless tobacco, snus, nicotine pouches, electronic nicotine delivery systems (ENDS) and medicinal nicotine. The point exchange system will be reviewed and the subjects are shown how to access product information on the webpage. They will then choose their preferred products and are instructed to only use the products they put in their “cart” in exchange for their points.

C.2 Dispense Study Product

After subject has selected their desired products (usual brand cigarettes and alternative nicotine products) from the Marketplace website, those products will be provided to the subject with instruction on how to track the use of their products for the Daily Call Recording System.

C.3 Product Accountability (Dispensing Log)

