5.2.3. Phase 2: Marketplace Adaptation Visit MP (91) Procedures

A. *Physiological Measures at MP 91:*

- 1) BrAC (discontinued at telehealth visits).
- 2) Expired breath CO level.
- 3) Vitals signs (blood pressure, heart rate).
- 4) Weight.

B. Questionnaires and Assessments at MP 91:

B.1 Web-based data collection program completed by the subject:

- 1) Minnesota Nicotine Withdrawal Scale (MNWS).
- 2) Questionnaire of Smoking Urges-Brief -Usual Cigarette (QSU).
- 3) Cigarette & Product Evaluation Scale – (Baseline Usual Brand CES/PES).
- 4) Respiratory and Global Health Questionnaire.
- 5) If monitored for psychiatric illness: Beck Depression Inventory 2nd Edition (BD-II) (paper only).

B.2 Administered as an interview by the study Research Assistant (entered into REDCap):

- 1) Health Changes Questionnaire.
- 2) Adverse Events.
- 3) Concomitant Medications.
- 4) Review of Daily Call and follow-up on missing and unusual reports.
- 5) Timeline Followback Questionnaire (since last visit).
- 6) Product Accountability: Complete Product Dispensing Log.
- 7) Study Product and Procedure Compliance Review.
- 8) End of Visit Questionnaire.

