16.6.5. Exploratory Endpoint Analysis

We will conduct the following exploratory endpoint analysis:

- For the number of days of non-combusted tobacco/nicotine products use, we will use Poisson or negative binomial regression, adjusting for baseline value, study site, whether the visit is pre-COVID or not, and any baseline characteristics which are different at $p<0.20$.
- Descriptively examine the characteristics of the various products that are chosen (type, nicotine strength, flavor).
- Other biomarkers will be analyzed similar to the Secondary Endpoint analysis.
- Product satisfaction (Product Evaluation Scale, Cigarette Evaluation Scale) at the first time a participant tried a product will be summarized using mean and standard deviation and compared between two treatment arms using linear regression.
- Repeated measure of perceived health risk will be analyzed using the mixed effects model as described in the Secondary Analysis Section.
- Discomfort as assessed by MNWS-R, QSU, and CES-D will be compared between the VLNC vs. NNC cigarette conditions. The methods for comparing discomfort measures between VLNC and NNC cigarettes will be the same as for those described for the Primary Endpoints.
- Repeated measures of dependence of study cigarettes will be analyzed using mixed effects model described in the Secondary Analysis Section.
- Examine the cross-sectional associations of non-combusted products use with cigarettes smoked and biomarkers at different visits using marginal generalized estimating equations (GEE) model⁶² (Chapter 12) with the non-combusted product use as the independent variable.
- We will explore baseline predictors of responses. We will use multivariable regressions to determine predictors of product use patterns, e.g., non-combusted product use, combusted product use, and smoke-free days. Predictor variables (depending on the responses measured) will include baseline CPD, total nicotine equivalents, FTND, age, sex, racial ethnic group, SES, perceived risk of products, product expectancy, product utility, social and environmental influences, contemplation ladder, menthol cigarette use and nicotine metabolite ratio (NMR, reflecting rate of nicotine metabolism). Similar regression models as described in Primary and Secondary Endpoint Analyses will be used.

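### The between-arm comparison of product ratings at first try is not limited to Phase 3, so as worded it can include ratings made before randomisation

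*Combined protocol and SAP*

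**What the plan says.** **The rule.** Under SAP 6.5, product satisfaction (PES and CES) "at the first time a participant tried a product will be summarized using mean and standard deviation and compared between two treatment arms", by linear regression. Protocol 16.6.5 repeats it: "at the first time a participant tried a product will be summarized using mean and standard deviation". Neither names a phase. The endpoint definitions (SAP 5.3, protocol 3.3 and 16.5.3) tie a PES rating to use since the last visit and name no phase either. The neighbouring endpoint, days of non-combusted product use, does name Phase 3.

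**Access before randomisation.** Protocol 5.2.2 C says that after Visit 92 "subjects will have access to the web-based experimental marketplace that includes their usual brand cigarettes and non-combusted tobacco and nicotine products". Under protocol 4.2.1 the points allowance covers baseline use "plus 1 point per day to allow for experimentation in the marketplace", and "points per day are constant throughout the study". The experimentation allowance therefore applies in Phase 2 as well as Phase 3.

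**Ratings before randomisation.** The PES is given at MP 91 and MP 00 (protocol 5.2.3, 5.2.4 and the Section 27 procedure table). Participants are randomised at the end of Visit 00 (protocol 5.2.4).

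**Hints of intent.** The Phase 2 form is labelled "Baseline Usual Brand CES/PES", while the Phase 3 label refers to study cigarettes. The procedure table, however, has a single PES row running through both phases.

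**The concern.** Secondary Aim 1 (protocol 1.2.a) predicts that, among those who try them, non-combusted products will be rated better in the VLNC arm than in the NNC arm. That is an effect of assignment and can appear only in ratings made after it. In ratings made at MP 91 or MP 00 the expected arm difference is zero. If the first-try rule admits them, the estimate is a blend of the effect of interest and zero. The SAP 6.5 bullet is the only stated between-arm analysis of PES or CES ratings, so no other planned analysis of these scales would show the undiluted difference.

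The wording also leaves a choice open. The first rating ever given, the first Phase 3 rating of any product, and the first rating of a product new in Phase 3 are different data sets, and the text does not choose among them.

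**Working it through.** **Order of events.** Visit 92 ends and non-combusted products become available; PES at MP 91; PES at MP 00; randomisation at the end of Visit 00; Phase 3 PES ratings. A product first tried between Visit 92 and Visit 00 has its first rating before assignment. Study cigarettes are not offered in Phase 2 (Study Synopsis), so their ratings are not affected.

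**Inputs.** The plan gives no sample size, effect size or power for product ratings, so there is no stated figure to reproduce. Every value below is an assumption, used only to show scale.

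- d: VLNC minus NNC mean rating among products first tried in Phase 3.
- c: NNC mean among Phase 3 first tries minus the mean among Phase 2 first tries.
- fN, fV: share of first tries that fall in Phase 2, by arm.
- r: VLNC to NNC ratio of Phase 3 first tries per head.

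**Expected difference under the literal rule.** The Phase 2 first-try mean m is the same in both arms by randomisation. With M the NNC Phase 3 first-try mean, so that c = M − m:

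- VLNC mean = fV·m + (1−fV)(M + d)
- NNC mean = fN·m + (1−fN)·M
- Difference = (1−fV)·d + (fN−fV)·c

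Phase 2 tries per head are also balanced by randomisation, so fV = fN / (fN + r(1−fN)). For fN = 0.3 and r = 1.5, fV = 0.3/(0.3 + 1.05) = 0.222, and 1 − 0.222 = 78% of d is kept.

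**Precision of dropping Phase 2 first tries.** Assume equal SD, independent ratings and c = 0, and scale NNC first tries to 1:

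- SE, literal rule ∝ √(1 + 1/(fN + r(1−fN)))
- SE, Phase 3 first tries only ∝ √(1/(1−fN) + 1/(r(1−fN)))
- z ratio (Phase 3 only over literal) = [1/(1−fV)] × SE literal / SE Phase 3 only

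For fN = 0.3 and r = 1.5: (1/0.778) × √1.741/√2.381 = 1.286 × 1.319/1.543 = 1.10.

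| fN | r | fV | Share of d kept | (fN−fV)·c at c = ±0.5 SD | z ratio (c = 0) |
|---|---|---|---|---|---|
| 0.3 | 1 | 0.300 | 70% | 0 | 1.20 |
| 0.3 | 1.5 | 0.222 | 78% | ±0.039 SD | 1.10 |
| 0.3 | 2 | 0.176 | 82% | ±0.062 SD | 1.05 |
| 0.5 | 1 | 0.500 | 50% | 0 | 1.41 |
| 0.5 | 1.5 | 0.400 | 60% | ±0.050 SD | 1.22 |
| 0.5 | 2 | 0.333 | 67% | ±0.083 SD | 1.12 |

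At an equal share of 0.1, 90% is kept and the z ratio is 1/√0.9 = 1.05. The composition term takes the sign of c when VLNC uptake is higher, and the sign of c is not known. One participant may rate several products, so the z ratios are indicative only.

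**The case against.** The strongest reply is that the harmful reading is the less likely one. The sentence compares treatment arms, the hypothesis concerns the VLNC and NNC conditions, those conditions exist only in Phase 3, and the Phase 2 form is labelled as baseline. A reader might infer that the authors plan to compare arms on pre-randomisation ratings. The documents do not support that; what they show is a missing qualifier. The reply does not remove the defect, because no section supplies the qualifier and the rule, applied as written, admits the Phase 2 ratings.

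The size is also easily overstated. The largest losses (30% and 50%) require equal Phase 3 uptake in the two arms, whereas the trial hypothesises greater uptake under VLNC, which reduces the loss. Protocol 5.2.4 also expects experimentation to be concentrated early in the intervention, so the Phase 2 share may be small. Both points stand.

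Two further inferences go too far.

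- The design admits people who already use other products: the points "cover their baseline cigarettes and other nicotine product use (e.g., vaping device, smokeless tobacco or nicotine replacement therapies") and protocol 2.3 argues for "the need to conduct a study that includes a more broadly selected sample of smokers". Because no PES is given before MP 91, a reader might say that the rule selects nothing for such products. That is over-literal: the endpoint is rated whenever the product was used since the last visit, so the first time can mean the first rated use in the study.
- A reader might say that this is the only between-arm comparison of any product rating. It is the only one for PES and CES; perceived health risk is also rated by product and modelled with a treatment term (SAP 6.5 and 6.3.2).

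**Conclusion.** The point holds as a defect of wording with a real but unquantified effect. Applied literally, the first-try rule keeps only (1−fV) of the Phase 3 difference and adds a composition term of unknown sign. On assumed NNC Phase 2 shares of 0.3 and 0.5, and VLNC uptake from equal to twice that of NNC, 70% to 82% and 50% to 67% of the difference remain. Dropping Phase 2 first tries would raise z by a factor of 1.05 to 1.20 and 1.12 to 1.41 respectively, given equal SDs, independent ratings and c = 0. The documents supply none of these shares or ratios, so no single value should be quoted as the expected loss.

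Severity is low. The comparison is exploratory and tested without multiplicity adjustment (SAP 6.1). The primary endpoints, the secondary endpoints and the study-cigarette ratings are not affected.

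**What to change.** In SAP 6.5 and protocol 16.6.5, restrict the between-arm comparison to ratings made after randomisation, and report Phase 2 ratings descriptively as baseline. The authors should choose one of two versions as the main analysis and keep the other as a sensitivity analysis:

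- (a) the first Phase 3 rating of each product, adjusted for Phase 2 use (yes/no) and, where available, the Phase 2 rating; or
- (b) the first rating of products not used in Phase 2.

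The documents do not settle which is better. Version (a) is closer to what the form labels suggest; version (b) keeps the idea of a first try within the marketplace. The text should also state the level at which a product is defined (class, brand or flavour), since otherwise a second e-cigarette brand taken up in Phase 3 cannot be classified, and say how products used before the study are handled. For the CES, use the first study-cigarette rating.

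The cost is a short edit in two places and one extra analysis on data already collected. Version (b) uses fewer ratings: at equal shares of 0.3 or 0.5 its standard error rises by a factor of 1/√0.7 = 1.20 or 1/√0.5 = 1.41. In version (a), a product tried in Phase 2 contributes only if its use continued into Phase 3. Both versions still condition on the post-randomisation choice to use a product, as the present rule does for products tried in Phase 3, so neither is a fully randomised contrast. The text should say so.
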